### **14.3. Record Retention**

Essential documents must be retained by the investigator according to the period of time outlined in the clinical trial agreement. The investigator must retain these documents for the time period described above or according to local laws or requirements, whichever is longer. Essential documents include, but are not limited to, the following:

- Signed ICFs for all subjects;
- Subject identification code list, screening log (if applicable), and enrollment log;
- Record of all communications between the investigator and the IRB/EC;
- Composition of the IRB/EC;
- Record of all communications between the investigator, Celgene, and their authorized representative(s);
- List of Sub-investigators and other appropriately qualified persons to whom the investigator has delegated significant study-related duties, together with their roles in the study, curriculum vitae, and their signatures;
- Copies of CRFs (if paper) and of documentation of corrections for all subjects;
- IP accountability records;
- Record of any body fluids or tissue samples retained;
- All other source documents (subject records, hospital records, laboratory records, etc.);

- All other documents as listed in Section 8 of the ICH consolidated guideline on GCP (Essential Documents for the Conduct of a Clinical Trial).

The investigator must notify Celgene if he/she wishes to assign the essential documents to someone else, remove them to another location or is unable to retain them for a specified period. The investigator must obtain approval in writing from Celgene prior to destruction of any records. If the investigator is unable to meet this obligation, the investigator must ask Celgene for permission to make alternative arrangements. Details of these arrangements should be documented.

All study documents should be made available if required by relevant health authorities. The investigator or institution should take measures to prevent accidental or premature destruction of these documents.

## **15. QUALITY CONTROL AND QUALITY ASSURANCE**

All aspects of the study will be carefully monitored by Celgene or its authorized representative for compliance with applicable government regulations with respect to current GCP and SOPs.

### **15.1. Study Monitoring and Source Data Verification**

Celgene ensures that appropriate monitoring procedures are performed before, during and after the study. All aspects of the study are reviewed with the investigator and the staff at a study initiation visit and/or at an investigators' Meeting. Prior to enrolling subjects into the study, a Celgene representative will review the protocol, eCRFs, procedures for obtaining informed consent, record keeping, and reporting of AEs/SAEs with the investigator. Monitoring will include on-site visits with the investigator and his/her staff as well as any appropriate communications by mail, email, fax, or telephone. During monitoring visits, the facilities, investigational product storage area, eCRFs, subject's source documents, and all other study documentation will be inspected/reviewed by the Celgene representative in accordance with the Study Monitoring Plan.

Accuracy will be checked by performing source data verification that is a direct comparison of the entries made onto the eCRFs against the appropriate source documentation. Any resulting discrepancies will be reviewed with the investigator and/or his/her staff. Any necessary corrections will be made directly to the eCRFs or via queries by the investigator and/or his/her staff. Monitoring procedures require that informed consents, adherence to inclusion/exclusion criteria and documentation of SAEs and their proper recording be verified. Additional monitoring activities may be outlined in a study-specific monitoring plan.

### **15.2. Audits and Inspections**

In addition to the routine monitoring procedures, a Good Clinical Practice Quality Assurance unit exists within Celgene. Representatives of this unit will conduct audits of clinical research activities in accordance with Celgene SOPs to evaluate compliance with Good Clinical Practice guidelines and regulations.

The investigator is required to permit direct access to the facilities where the study took place, source documents, eCRFs and applicable supporting records of study subject participation for audits and inspections by IRB/ECs, regulatory authorities (eg, Food and Drug Administration [FDA], European Medicines Agency [EMA], Health Canada) and company authorized representatives. The investigator should make every effort to be available for the audits and/or inspections. If the investigator is contacted by any regulatory authority regarding an inspection, he/she should contact Celgene immediately.

## 16. PUBLICATIONS

As described in Section 13.2, all protocol- and amendment-related information, with the exception of the information provided by Celgene on public registry websites, is considered Celgene confidential information and is not to be used in any publications. Celgene protocol-related information proposed for use in a publication must be submitted to Celgene for review and approval, and should not be utilized in a publication without express written approval from Celgene, or as described in the Clinical Trial Agreement.

[figure not shown]
Celgene will ensure Celgene-sponsored studies are considered for publication in the scientific literature in a peer-reviewed journal, irrespective of the results. At a minimum, this applies to results from all Phase 3 clinical studies, and any other study results of significant medical importance. This also includes results relating to investigational medicines whose development programs have been discontinued.

Study results may also be presented at one or more medical congresses, and may be used for scientific exchange and teaching purposes. Additionally, this study and its results may be submitted for inclusion in all appropriate health authority study registries, as well as publication on health authority study registry websites, as required by local health authority regulations.

[figure not shown]
Eligibility for external authorship, as well as selection of first authorship, will be based on several considerations, including, but not limited to, contribution to protocol development, study recruitment, data quality, participation in data analysis, participation in study steering committee (when applicable) and contribution to abstract, presentation and/or publication development.

## 18. APPENDICES

### Appendix A: Table of Abbreviations

**Table 4: Abbreviations and Specialist Terms**

Abbreviation or Specialist Term	Explanation
ACS	Acute coronary syndrome
AE	Adverse event
ALP	Alkaline phosphatase
ALT	Alanine aminotransferase (SGPT)
AML	Acute myeloid leukemia
ANC	Absolute neutrophil count
AST	Aspartate aminotransferase (SGOT)
BCRP	Breast cancer resistance protein
β-hCG	β-subunit of human chorionic gonadotropin
BID	Twice a day
BP	Blood pressure
BMA	Bone marrow aspirate
BMB	Bone marrow biopsy
BSA	Body surface area
BSC	Best supportive care
BUN	Blood urea nitrogen
CBC	Complete blood count
CCR	Conventional care regimen
CI	Confidence interval
CML	Chronic myelogenous leukemia
CNS	Central nervous system
CO 2	Carbon dioxide
CR	Morphologic complete remission
CRh	Morphologic complete remission with partial hematologic recovery
CRi	Morphologic complete remission with incomplete neutrophil recovery
CRp	Morphologic complete remission with incomplete platelet recovery

**Table 4: Abbreviations and Specialist Terms (Continued)**

Abbreviation or Specialist Term	Explanation
CTCAE	Common Terminology Criteria for Adverse Events
CV	Coefficient of variation
CYP	Cytochrome
DNA	Deoxyribonucleic acid
DMC	Data Monitoring Committee
EBV	Epstein-Barr virus
EC	Ethics Committee
ECG	Electrocardiogram
ECHO	Echocardiogram
ECOG	Eastern Cooperative Oncology Group
eCRF	Electronic case report form
EEA	European Economic Area
EFS	Event-free survival
EMA	European Medicines Agency
EORTC	European Organization for Research and Treatment of Cancer
EOT	End of treatment
FCBP	Female of childbearing potential
FDA	Food and Drug Administration
GCP	Good Clinical Practice
G-CSF	Granulocyte-colony stimulating factor
GFR	Glomerular filtration rate
GGT	Gamma glutamyl transpeptidase
GI	Gastrointestinal
GM-CSF	Granulocyte macrophage colony-stimulating factor
GVHD	Graft-versus-host disease
HBV	Hepatitis B virus
HCV	Hepatitis C virus

**Table 4: Abbreviations and Specialist Terms (Continued)**

Abbreviation or Specialist Term	Explanation
HDPE	High density polyethylene
HI	Hematologic improvement
HI-E	Hematologic improvement erythroid response
HI-N	Hematologic improvement neutrophil response
HI-P	Hematologic improvement platelet response
HIV	Human immunodeficiency virus
HR	Hazard ratio
HRQoL	Health-related Quality-of-Life
HSCT	Hematopoietic stem cell transplantation
IB	Investigator's Brochure
ICF	Informed consent form
ICH	International Council on Harmonisation
IDAC	Intermediate-dose cytarabine
IDH	Isocitrate dehydrogenase
IDH2	Isocitrate dehydrogenase 2
IND	Investigational New Drug
INR	International normalized ratio
IP	Investigational product
IRAC	Independent Response Assessment Committee
IRB	Institutional Review Board
ITT	Intent-to-treat
IV	Intravenously
IVRS	Interactive voice response system
IWG	International Working Group
KM	Kaplan-Meier
LDAC	Low-dose cytarabine
LDL-C	Low-density lipoprotein cholesterol

**Table 4: Abbreviations and Specialist Terms (Continued)**

Abbreviation or Specialist Term	Explanation
LDH	Lactate dehydrogenase
LVEF	Left ventricular ejection fraction
MDS	Myelodysplastic syndromes
MCH	Mean corpuscular hemoglobin
MCHC	Mean corpuscular hemoglobin concentration
MCV	Mean corpuscular volume
MDRD	Modification of Diet in Renal Disease
MedDRA	Medical Dictionary for Regulatory Activities
mITT	Modified intent-to-treat
MLFS	Morphologic leukemia-free state
MPN	Myeloproliferative neoplasm
MUGA	Multi-gated acquisition
NCCN	National Comprehensive Cancer Network
NCI	National Cancer Institute
NIP	Non-investigation product
NYHA	New York Heart Association
OAT	Organic anion transporter
ORR	Overall response rate
OS	Overall survival
PCR	Polymerase chain reaction
PD	Progressive disease
P-gp	P-glycoprotein

**Table 4: Abbreviations and Specialist Terms (Continued)**

Abbreviation or Specialist Term	Explanation
PO	Orally
PR	Partial remission
PT	Prothrombin time
PTT	Partial thromboplastin time
QD	Once a day
QTc	Heart rate-corrected QT
QTcF	QTc with Fridericia's correction
RBC	Red blood cell
SAE	Serious adverse event
SAP	Statistical analysis plan
SC	Subcutaneous
SD	Stable disease
SDev	Standard deviation
SGOT	Serum glutamic oxaloacetic transaminase
SGPT	Serum glutamic pyruvic transaminase
SmPC	Summary of Product Characteristics
SOP	Standard operating procedure
SUSAR	Suspected unexpected serious adverse reaction
UDP	Uridine diphosphate
UGT1A1	UDP-glucuronosyltransferase 1 family, polypeptide A1
UK	United Kingdom
ULN	Upper limit of normal
US	United States
WBC	White blood cell

**Table 4: Abbreviations and Specialist Terms (Continued)**

Abbreviation or Specialist Term	Explanation
WHO	World Health Organization

## **Appendix B: World Health Organization Classification of Acute Myeloid Leukemia**

### **Acute myeloid leukemia with recurrent genetic abnormalities**

- Acute myeloid leukemia with t(8;21)(q22;q22); (RUNX1-RUNX1T1)
- Acute myeloid leukemia with inv(16)(p13.1q22) or t(16;16)(p13.1;q22); (CBFB-MYH11)
- Acute promyelocytic leukemia with t(15;17)(q22;q12); (PML-RARA)
- Acute myeloid leukemia with t(9;11)(p22;q23); MLLT3-MLL
- Acute myeloid leukemia with t(6;9)(p23q34); DEK-NUP214
- Acute myeloid leukemia with inv(3)(q21q26.2) or t(3;3)(q26.2); RPN1-EVI1
- Acute myeloid leukemia (megakaryoblastic) with t(1;22)(p13;q13); RBM15-MKL1
- Acute myeloid leukemia with gene mutations

### **Acute myeloid leukemia with myelodysplasia-related changes**

#### **Therapy-related myeloid neoplasma**

#### **Acute myeloid leukemia, not otherwise categorized**

- Acute myeloid leukemia with minimal differentiation
- Acute myeloid leukemia without maturation
- Acute myeloid leukemia with maturation
- Acute myelomonocytic leukemia
- Acute monoblastic and monocytic leukemia
- Acute erythroid leukemia (erythroid/myeloid and pure erythroleukemia)
- Acute megakaryoblastic leukemia
- Acute basophilic leukemia
- Acute panmyelosis with myelofibrosis

Source: [Swerdlow, 2008](#).

## Appendix C: Acute Myeloid Leukemia Risk Status

Risk Status	Cytogenetics	Molecular Abnormalities a
Better-risk	inv(16) b, c t(16;16) b t(8;21) b t(15;17)	Normal cytogenetics: NPM1 mutation in the absence of FLT3-ITD or isolated biallelic CEBPA mutation
Intermediate-risk	Normal cytogenetics +8 t(9;11) Other non-defined	t(8;21), inv(16), t(16;16): with c-KIT d mutation
Poor-risk	Complex ( $\geq 3$ clonal chromosomal abnormalities) Monosomal karyotype -5, 5q-, -7, 7q- 11q23 - non t(9;11) inv(3), t(3;3) t(6;9) t(9;22) e	Normal cytogenetics: with FLT3-ITD mutation f

a The molecular abnormalities included in this table reflect those for which validated assays are available in standardized commercial laboratories. Given the rapidly evolving field, risk stratification should be modified based on continuous evaluation of research data. Other novel genetic mutations have been identified that may have prognostic significance.

b Other cytogenetic abnormalities in addition to these findings do not alter risk status.

c Paschka P, Du J, Schlenk RF, Gaidzik VI, Bullinger L, Corbacioglu A, et al. Secondary genetic lesions in acute myeloid leukemia with inv(16) or t(16;16): a study of the German-Austrian AML study group (AML5G). *Blood* 2013; 121:170-177.

d Emerging data indicates the presence of c-KIT mutation in subjects with t(8;21), and to a lesser extent, inv(16), confers a high risk of relapse. These subjects should be considered for clinical trials, if available.

e For Philadelphia+ acute myeloid leukemia (AML) t(9;22), manage as myeloid blast crisis in chronic myeloid leukemia (CML), with addition of tyrosine kinase inhibitors. These subjects are excluded from study entry.

f FLT3-ITD mutations are considered to confer a significant poor outcome in subjects with normal karyotype, and these subjects should be considered for clinical trials where available. There is controversy as whether FLT3-TKD mutations carry equally poor prognosis

Source:

National Comprehensive Cancer Network Clinical Practice Guidelines in Oncology for Acute Myeloid Leukemia. National Comprehensive Cancer Network website. Available at [http://www.nccn.org/professionals/physician\\_gls/PDF/aml.pdf](http://www.nccn.org/professionals/physician_gls/PDF/aml.pdf). Accessed 05 Aug 2015.

## Appendix D: Eastern Cooperative Oncology Group (ECOG) Performance Status

Eastern Cooperative Oncology Group (ECOG) Performance Status	
Grade	ECOG
0	Fully active, able to carry on all pre-disease performance without restriction.
1	Restricted in physically strenuous activity but ambulatory and able to carry out work of a light or sedentary nature, eg, light house work, office work.
2	Ambulatory and capable of all selfcare but unable to carry out any work activities. Up and about more than 50% of waking hours.
3	Capable of only limited selfcare, confined to bed or chair more than 50% of waking hours.
4	Completely disabled. Cannot carry on any selfcare. Totally confined to bed or chair.
5	Dead.

Source: [Oken, 1982](#).

## Appendix E: New York Heart Association Classification for Congestive Heart Failure

Functional Capacity
Class I. Subjects with cardiac disease but without resulting limitation of physical activity. Ordinary physical activity does not cause undue fatigue, palpitation, dyspnea, or anginal pain.
Class II. Subjects with cardiac disease resulting in slight limitation of physical activity. They are comfortable at rest. Ordinary physical activity results in fatigue, palpitation, dyspnea, or anginal pain.
Class III. Subjects with cardiac disease resulting in marked limitation of physical activity. They are comfortable at rest. Less than ordinary activity causes fatigue, palpitation, dyspnea, or anginal pain.
Class IV. Subjects with cardiac disease resulting in inability to carry on any physical activity without discomfort. Symptoms of heart failure or the anginal syndrome may be present even at rest. If any physical activity is undertaken, discomfort is increased.

Source: [American Heart Association, 1994](#).

## Appendix F: International Working Group Acute Myeloid Leukemia Response Criteria

Hematologic Response According to modified IWG Criteria for AML	
Category	Definition
Morphologic Complete Remission (CR)	Defined as less than 5% blasts in a BM aspirate sample with marrow spicules and with a count of at least 200 nucleated cells. There should be no blasts with Auer rods and absence of extramedullary disease. Plus, all the following conditions should be met: 
 
ANC <math>\geq 1 \times 10^9/L</math> (1,000/<math>\mu</math>L)
 
Platelet count <math>\geq 100 \times 10^9/L</math> (100,000/<math>\mu</math>L)
 
Independent of red cell transfusions for <math>\geq 1</math> week immediately before each response assessment
 

Morphologic Complete Remission with Incomplete Neutrophil Recovery (CRi)a	Defined as all criteria of CR except the following: 
 
ANC <math>< 1 \times 10^9/L</math> (1,000/<math>\mu</math>L)
 

Morphologic Complete Remission with Incomplete Platelet Recovery (CRp)a	Defined as all criteria of CR except the following: 
 
Platelet count <math>< 100 \times 10^9/L</math> (100,000/<math>\mu</math>L)
 

Morphologic Complete Remission with Partial Hematologic Recovery (CRh)a	Defined as all criteria of CR except the following: 
 
ANC <math>> 0.5 \times 10^9/L</math> (500/<math>\mu</math>L); and
 
Platelet count <math>> 50 \times 10^9/L</math> (50,000/<math>\mu</math>L)
 

Morphologic Leukemia-free State (MLFS)	Defined as less than 5% blasts in a BM aspirate sample with marrow spicules and with a count of at least 200 nucleated cells. There should be no blasts with Auer rods and absence of extramedullary disease
Partial Remission (PR)	Defined as all hematologic criteria of CR with a $> 50\%$ decrease in the percentage of BM blasts to 5% to 25% (a blast count value of $< 5\%$ may also be considered a partial remission if Auer rods are present) b
Cytogenetic Complete Remission (CRc)	Defined as CR/CRi/CRp with a reversion to a normal karyotype in cases with an abnormal karyotype at baseline, based on evaluating $\geq 20$ metaphase BM cells
Morphologic Relapse after CR/CRi/CRpa	Defined as one of the following conditions: 
 
Reappearance of <math>\geq 5\%</math> blasts in the BM not attributable to any other cause (eg, BM regeneration after consolidation therapy); or
 
Development of extramedullary disease
 

Not evaluable (NE)a	Defined as without a posttreatment response assessment
Stable Disease (SD)a	Defined as failure to meet any of the above criteria and not meeting the criteria of progressive disease (see below)
Progressive Disease (PD)a	Defined as one of the following conditions: 
 
For subjects with 5 to 70% BM blasts at baseline: a <math>> 50\%</math> increase of BM blast count percentage from baseline to <math>\geq 20\%</math>; or
 
For subjects with <math>> 70\%</math> BM blasts at baseline: a doubling of absolute blast count in peripheral blood from baseline to <math>\geq 10 \times 10^9/L</math> (10,000/<math>\mu</math>L); or
 
Development of new extramedullary disease since last response assessment
 
 Progressive disease is to be confirmed by 2 consecutive response assessments separated by at least 1 month. The date of progressive disease is defined as the first date that one of three conditions listed above was met.

AML = Acute Myeloid Leukemia; ANC= Absolute Neutrophil Count; BM= Bone Marrow; IWG= International Working Group.

a Modification to IWG response criteria. Note: CRh is not available for the investigator's assessment and will be assessed by the Sponsor only and based on laboratory dataset.

b If the pre-treatment bone marrow blast percentage was 50% to 100%, the percentage of blasts must decrease to a value between 5% and 25%; if the pre-treatment blast percentage was 20% to less than 49%, they must decrease by at least half to a value of more than 5%.

Notes: Deletions to the IWG response criteria are not shown.

Source: [Cheson, 2003](#).

## Appendix G: Definitions of Prior Line of AML Therapy

A line of AML therapy is defined as cytotoxic chemotherapy or low-intensity therapy, single agent or in combination, delivered with the intent to induce remission and/or prolong survival.

If remission is not induced by the first cycle (eg, cytarabine 100-200 mg/m^2 continuous infusion for 7 days), the second cycle is modified (eg, cytarabine 1 to 3 g/m^2 every 12 hours for 3 to 7 days) with the intent to induce remission, then the subject has received two different lines of AML therapy. Treatment modifications with the intent to manage toxicity are not counted as separate lines.

The line used for re-induction for first relapse is also regarded as a second line even if the same drugs are given at the same doses as for the first remission induction, since the disease characteristics have changed from diagnosis to relapse.

Post-remission strategies (regimens) such as consolidation or maintenance are not counted as separate lines.

Transplantation is considered as a line if given with the intent to induce remission. However, transplantation as a post-remission strategy is not considered a separate line as it is regarded as consolidation.

Hydroxyurea is not counted as a separate line.

Note that, for subjects having AML secondary to prior higher risk (Intermediate-2 or High risk according to the International Prognostic Scoring System [see below]) MDS treated with a hypomethylating agent [eg, azacitidine or decitabine], the hypomethylating therapy can be counted as a line if there is disease progression to AML during or shortly (eg, within 60 days) after the hypomethylating therapy.

International Prognostic Scoring System for MDS					
Prognostic Variable	Score Value				
	0	0.5	1.0	1.5	2.0
Bone Marrow Blasts (%)	< 5	5-10	-	11-20	21-30
Karyotype a	Good	Intermediate	Poor	-	-
Cytopenias b	0 or 1	2 or 3	-	-	-

a Good: normal, -Y, del(5q), del(20q); Poor: complex (≥ 3 abnormalities) or chromosome 7 anomalies; Intermediate: other abnormalities.

b Defined as: Hemoglobin < 100 g/L, absolute neutrophil count < 1.5 x 10^9/L, and platelet count < 100 x 10^9/L.

Note: Scores for risk groups are as follows: Low = 0; INT-1 = 0.5-1.0; INT-2 = 1.5-2.0; and High: ≥ 2.5.

Source: [Greenberg, 1997](#).

## Appendix H: Hematologic Improvement According to the International Working Group for Myelodysplastic Syndromes

Hematologic Improvement According to IWG Criteria	
Hematologic improvementa	Response criteria (responses must last at least 8 week)b
Erythroid Response (HI-E) (pre-treatment, < 11 g/dL)	
 
• Hemoglobin increase by <math>\geq 1.5</math> g/dL
 
• Relevant Reduction in units of RBC transfusions by an absolute number of at least 4 RBC transfusions/8 week compared with the pretreatment transfusion number in the previous 8 week
 
 
Note: Only RBC transfusions given for a hemoglobin of <math>\leq 9.0</math> g/dL on treatment will count in the RBC transfusion response evaluationb

Platelet Response (HI-P) (pre-treatment, < 100 X 10  /L)	
 
• Absolute increase of <math>\geq 30 \times 10^9/L</math> for subjects starting with <math>> 20 \times 10^9/L</math> platelets
 
• Increase from <math>< 20 \times 10^9/L</math> to <math>> 20 \times 10^9/L</math> and by at least 100%b
 

Neutrophil Response (HI-N) (pre-treatment, < 1.0 X 10  /L)	
 
• At least 100% increase and an absolute increase <math>> 0.5 \times 10^9/L^b</math>
 

Progression or Relapse After HI c	
At least 1 of the following:
 
 
• At least 50% decrease from maximum response levels in granulocytes or platelets
 
• Reduction in hemoglobin by <math>\geq 1.5</math> g/dL
 
• Transfusion dependence
 

HI-E = hematologic improvement erythroid response; HI-N = hematologic improvement neutrophil response; HI-P = hematologic improvement platelet response; IWG = International Working Group; RBC = red blood cell.

- a Pre-treatment counts averages of at least 2 measurements (not influenced by transfusions, ie, no RBC transfusions for 2 weeks and no platelet transfusions for 1 week)  $\geq 1$  week apart (modification).
- b Modification to IWG (2000) response criteria.
- c In the absence of another explanation, such as acute infection, repeated courses of chemotherapy (modification), gastrointestinal bleeding, hemolysis, and so forth. It is recommended that the 2 kinds of erythroid and platelet responses be reported overall as well as by the individual response pattern.

Note: Deletions to the IWG response criteria are not shown. To convert hemoglobin levels from grams per deciliter to grams per liter, multiply grams per deciliter by 10.

Source: [Cheson, 2006](#).

**Appendix I: European Organization for Research and Treatment of Cancer  
 Quality-of-Life questionnaire (Version 3.0) (Continued)**

During the past week:	Not at All	A Little	Quite a Bit	Very Much
17. Have you had diarrhea?	1	2	3	4
18. Were you tired?	1	2	3	4
19. Did pain interfere with your daily activities?	1	2	3	4
20. Have you had difficulty in concentrating on things, like reading a newspaper or watching television?	1	2	3	4
21. Did you feel tense?	1	2	3	4
22. Did you worry?	1	2	3	4
23. Did you feel irritable?	1	2	3	4
24. Did you feel depressed?	1	2	3	4
25. Have you had difficulty remembering things?	1	2	3	4
26. Has your physical condition or medical treatment interfered with your family life?	1	2	3	4
27. Has your physical condition or medical treatment interfered with your social activities?	1	2	3	4
28. Has your physical condition or medical treatment caused you financial difficulties?	1	2	3	4

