#### 9.6.2.2. Additional Secondary Efficacy Analyses

The other secondary endpoints include duration of response, time to response, rates of overall remission, CR and HI assessed by an IRAC according to modified IWG AML response criteria ([Appendix F](#)) and IWG MDS HI criteria ([Appendix H](#)), treatment mortality at 30 and 60 days, one-year survival, rate of HSCT and time to treatment failure. The definitions of these additional secondary efficacy endpoints are listed below and in Section 2.

**Duration of response** is defined as time from first documented MLFS/CR/CRi/CRp/ PR to documented morphologic relapse after CR/CRi/CRp/ PD or death due to any cause, whichever occurs first. Subjects without morphologic relapse, PD or death due to any cause will be censored at the date of the last response assessment.

**Time to response** is defined as time from randomization to first documented MLFS/CR/CRi/CRp/ /PR. Subjects without a MLFS/CR/CRi/CRp/ PR will be censored at the date of the last response assessment.

**Treatment mortality at 30 and 60 days** is defined as rate of death from any cause within 30 or 60 days of initiation of study treatment.

**One-year survival** is defined as the probability of survival at 1 year from randomization.

**Overall remission rate** is defined as rate of CR + CRi + CRp according to modified IWG AML response criteria ([Appendix F](#)).

**Complete remission rate** is defined as rate of CR according to modified IWG AML response criteria ([Appendix F](#)).

**Hematologic improvement rate** is defined as rate of neutrophil response (hematologic improvement neutrophil response [HI-N]) + platelet response (hematologic improvement platelet response [HI-P]) + erythroid response (hematologic improvement erythroid response [HI-E]) according to IWG MDS HI criteria ([Appendix H](#)).

**Rate of HSCT** is defined as rate of bridge-to-HSCT through study treatment.

**Time to treatment failure** is defined as time from randomization to discontinuation of study treatment due to any cause.

The rate of CR/CR with partial hematologic recovery (CRh; [Appendix F](#)) and duration of CR/CRh will be analyzed using the statistical methods mentioned above or other statistical methods as appropriate. Note: CRh is not available for the investigator's assessment and will be assessed by the Sponsor only and based on laboratory dataset.

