Neutrophil Response (HI-N) (pre-treatment, < $1.0 \times 10^9/L$)	
 At least 100% increase and an absolute increase $\geq 0.5 \times 10^9/L$ ^b
Progression or Relapse After HI	
At least 1 of the following:
 
 At least 50% decrease from maximum response levels in granulocytes or platelets Reduction in hemoglobin by ≥ 1.5 g/dL Transfusion dependence

HI-E = hematologic improvement erythroid response; HI-N = hematologic improvement neutrophil response; HI-P = hematologic improvement platelet response; IWG = International Working Group; RBC = red blood cell.

Pre-treatment counts averages of at least 2 measurements (not influenced by transfusions, i.e., no RBC transfusions for 2 weeks and no platelet transfusions for 1 week) ≥ 1 week apart (modification).

Modification to IWG (2000) response criteria.

^c In the absence of another explanation, such as acute infection, repeated courses of chemotherapy (modification), gastrointestinal bleeding, hemolysis, and so forth. It is recommended that the 2 kinds of erythroid and platelet responses be reported overall as well as by the individual response pattern.

Note: Deletions to the IWG response criteria are not shown. To convert hemoglobin levels from grams per deciliter to grams per liter, multiply grams per deciliter by 10.

Source: Cheson, 2006.

Celgene Signing Page

This is a representation of an electronic record that was signed electronically in Livelink.
This page is the manifestation of the electronic signature(s) used in compliance with
the organizations electronic signature policies and procedures.

UserName: [REDACTED]
Title: [REDACTED]
Date: Tuesday, 02 June 2020, 08:50 AM Eastern Daylight Time
Meaning: Approved, no changes necessary.
=====

UserName: [REDACTED]
Title: [REDACTED]
Date: Tuesday, 02 June 2020, 02:35 PM Eastern Daylight Time
Meaning: Approved, no changes necessary.
=====

UserName: [REDACTED]
Title: [REDACTED]
Date: Tuesday, 02 June 2020, 02:37 PM Eastern Daylight Time
Meaning: Approved, no changes necessary.
=====

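### The response criteria have an on-treatment rule for red-cell transfusion but none for platelet transfusion, and HI asks for transfusion-free counts only before treatment

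*Protocol*

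**What the plan says.** **HI (Protocol Appendix H; SAP Section 15.6).** The transfusion-free condition sits in a footnote on "Pre-treatment counts averages of at least 2 measurements", which must be "not influenced by transfusions, ie, no RBC transfusions for 2 weeks and no platelet transfusions for 1 week". The SAP carries the same windows: "no RBC transfusions for 2 weeks and no platelet transfusions for 1 week". On treatment, the table heading says that "responses must last at least 8 week", and the count branches ask for a hemoglobin rise of at least 1.5 g/dL (HI-E) or a stated platelet rise (HI-P). The one on-treatment transfusion note limits which red-cell transfusions "will count in the RBC transfusion response evaluation"; it governs the transfusion-reduction branch, not the hemoglobin branch. "Transfusion dependence" is listed as loss of HI. SAP Section 10.3.2.8 defines dependence for baseline only, as at least one transfusion in the 56 days before first dose.

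**Response (Protocol Appendix F; SAP Section 15.5).** CR requires ANC of at least 1 and platelets of at least 100 (x 10^9/L throughout), and that the subject be "Independent of red cell transfusions for" at least 1 week before each assessment. CRi, CRp and CRh keep every CR criterion except the stated count changes, and PR keeps the CR hematologic criteria. None mentions platelet transfusion.

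**Who derives it.** Protocol Section 9.6.2.2 says that CRh "will be assessed by the Sponsor only and based on laboratory dataset". SAP Sections 10.3.2 and 10.3.2.11 have CR/CRh assessed by the IRAC and also by a sponsor derivation. SAP Section 10.3.1 refers the IRAC procedures to a separate charter, which is not among the documents.

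**Use.** CR, HI and CR/CRh rates are each compared between arms by Fisher's exact test (SAP Sections 10.3.2.7, 10.3.2.8 and 10.3.2.11).

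**The concern.** The plan accepts in two places that a transfused count is not evidence of marrow recovery: red cells before each response assessment, and both products before the HI baseline. It leaves out platelet transfusion when a platelet threshold is judged on treatment, and both products when an on-treatment HI count is judged.

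Platelet and red-cell transfusions are permitted supportive care under institutional practice (Protocol Section 8.1). The trial is open-label and has four comparator options, so transfusion intensity could differ between groups. If it does, part of an observed difference in CR, CR/CRh or HI rate could reflect transfusion practice. Appendix F sets no minimum duration for CR or CRh, so one transfused platelet value on the assessment day can be enough.

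**Working it through.** The plan states no figure on this point, so there is none to reproduce. The check applies the written rules to illustrative subjects. The subject values are assumptions; the thresholds are from Appendices F and H.

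**Step 1: response.** Inputs to the rule are marrow blasts, ANC, platelets and red-cell independence for at least 1 week. Platelet transfusion is not an input, so a native and a transfused platelet count are treated alike.

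| Subject | Platelets 30 | Platelets 60 | Platelets 105 |
|---|---|---|---|
| Blasts 3%, ANC 1.2, no red cells in prior week | CRp | CRp, also meets CRh | CR |
| Blasts 3%, ANC 0.7, no red cells in prior week | MLFS | CRh | CRi, also meets CRh |
| Blasts 12% (assumed baseline 40%), ANC 1.2, no red cells in prior week | not PR | not PR | PR |
| Blasts 3%, ANC 1.2 or 0.7, red cells in prior week | MLFS | MLFS | MLFS |

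In the third row the blast fall is (40 - 12)/40 = 70%, to a value between 5% and 25%, so the marrow part of PR is met and platelets decide. The last row shows that the red-cell rule works as intended on treatment. In the first three rows, moving right by platelet transfusion alone changes the category. CRi cannot become CR this way, because those two differ in the neutrophil count.

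**Step 2: which endpoints move.**
- CR rate: CRp to CR.
- CR/CRh rate, and time to and duration of CR/CRh: CRp or MLFS into CR/CRh.
- Overall remission rate (CR + CRi + CRp): only MLFS to CRi.
- ORR (CR + CRi + CRp + PR + MLFS): CRp and MLFS already count, so only non-response to PR.
- OS: none.

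**Step 3: size per subject.** With 158 planned per arm and ITT denominators, one reclassified subject changes an arm's rate by 1/158 = 0.63 percentage points, and five by 5/158 = 3.2 points. Five is only a scale; the documents give no frequency.

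**Step 4: HI.** The count thresholds are met with or without transfusion: hemoglobin 7.0 to 8.5 g/dL is +1.5 (HI-E); platelets 15 to 30 is +100% and above 20 (HI-P); platelets 25 to 60 is +35, at least 30 (HI-P). The response must also last 8 weeks (8 x 7 = 56 days) without transfusion dependence. If the SAP's baseline definition were carried onto treatment, any transfusion of that product within those 56 days would end HI. If dependence meant regular support, a subject transfused intermittently could keep HI. The documents do not say which applies.

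**The case against.** Much of the case on the other side stands.

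- A reader might infer that any subject held above the HI thresholds by transfusion scores as improved. The documents do not support that. Sustained support for 8 weeks is naturally read as transfusion dependence, which Appendix H treats as loss of HI. What remains is that the term has no on-treatment definition.
- A reader might infer that subjects with no marrow recovery can be called CR or CRh. They cannot: blasts below 5%, the ANC threshold and red-cell independence are still required. Platelet transfusion moves subjects who already have a cleared marrow, or, for PR, a sufficient blast fall.
- A reader might infer that the sponsor derivation cannot check red-cell independence. No section describes what the laboratory dataset contains, and red-cell independence remains a criterion for CRh. It is only unstated how that criterion is checked.
- It cannot be said that no rule exists anywhere. The IRAC receives transfusion records for HI (Protocol Section 6.5.2), and its charter may contain a rule for HI and for response.
- The SAP tabulates 56-day red-cell and platelet transfusion independence by best response (Section 10.3.2.8). That would reveal some transfusion-supported remissions, but it does not change how they are classified.
- HI, CR and CR/CRh are outside the OS, ORR, EFS testing sequence (SAP Section 10.1), and supportive care is available in both arms.

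These points narrow the concern. They do not supply a platelet-transfusion condition in Appendix F or SAP Section 15.5.

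**Conclusion.** The point holds as a cheap improvement to secondary endpoint definitions. As written, CR, CRh, CRi and PR can rest on a platelet count supported by transfusion. That affects the CR and CR/CRh rates and the time to and duration of CR/CRh. It reaches ORR only through PR and does not touch OS. For HI the finding is weaker: sustained support may already be caught as dependence, while intermittent on-treatment support is not clearly excluded.

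This rests on the two documents alone and assumes that the IRAC Charter does not already close the gap. A reader might go further and infer a bias in favor of one arm. The documents give neither the frequency of transfused assessments nor a difference between arms, so neither the size nor the direction of any bias can be stated.

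**What to change.** In the SAP, before the final database lock:

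1. Require that platelet values used for CR, CRh, CRi and PR be free of platelet transfusion for 1 week, which is the window the plan already uses for HI baselines.
2. Derive the sponsor CR/CRh from the laboratory and transfusion records together, so that the red-cell and platelet conditions are both checked.
3. Apply the 2-week red-cell and 1-week platelet windows to on-treatment values used for the hemoglobin branch of HI-E and for HI-P.
4. Define transfusion dependence on treatment.

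If the IRAC Charter already has such a rule, cite it and match the sponsor derivation to it. If the definition now in Appendix F must be kept for comparability with other trials, report it as a sensitivity analysis.

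The cost is wording and a dataset merge. Transfusion type, units, reason and date are already collected from 8 weeks before treatment onward (Protocol Table 3, note u), and the SAP already derives transfusion-free intervals. The downside is that some assessments become non-evaluable and the rates may fall. Nothing here changes how subjects are transfused; it concerns only which counts enter the endpoint.
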